• Patients who were randomized on Protocol CL-PTL-119 and were subsequently unblinded at recurrence and were assigned to the placebo arm.

The primary objective of the study is to determine the safety of the Vigil and atezolizumab combination. Secondary objectives include determination of the immune response rate to Vigil alone, atezolizumab alone and the combination of the two agents. In patients with measureable disease, anti-tumor activity as assessed by RECIST 1.1 criteria, will also be summarized and correlated to baseline tumor mutation burden, baseline PD-L1 expression, post treatment TIL infiltration, change in PD-L1 expression and circulating tumor cell response. Overall assessment of time to progression and survival will also be summarized for each cohort. Assuming no untoward adverse effects from the combination of Vigil with atezolizumab, the treatment of 20-25 patients should be sufficient to assess safety and provide an estimate of the immune response rate and RECIST response rate.

Part 1

The first part will be a safety run-in where the initial 3 subjects registered will receive the combination of Vigil plus atezolizumab. Part 1 will evaluate the safety of Vigil in combination with atezolizumab.

Vigil immunotherapy will be administered at a concentration of 1x10⁷ cells/dose given via intradermal injection every 3 weeks for a minimum of 4 doses and a maximum of 12 doses. Atezolizumab will be administered at the FDA approved dose and schedule as described in the U.S. Package Insert (USPI). Thus, atezolizumab is to be administered at a dose of 1200mg as an intravenous infusion every 3 weeks. The initial dose is to be administered over one hour and if well tolerated, subsequent infusions may be administered over 30 minutes. Vigil should be administered first, followed 30 minutes later by atezolizumab.

The first subject to receive the combination of Vigil plus atezolizumab must complete the first 21-day cycle of combination therapy without serious, unexpected toxicity before the enrollment of any patients into Part 2 can occur.

Part 2

Part 2 is a randomized, open label intra-patient crossover study of Vigil, the checkpoint inhibitor atezolizumab and the combination of the two agents. Eligible patients will be randomized to receive two cycles of Vigil alone or two cycles of atezolizumab alone, followed by combination treatment with both agents.

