The primary objective of the study is to determine the safety of the Vigil and atezolizumab combination. Secondary objectives include determination of immune response rate to Vigil alone, atezolizumab alone and the combination of the two agents. In patients with measureable disease, anti-tumor activity as assessed by RECIST 1.1 criteria, will also be summarized and correlated to baseline tumor mutation burden, baseline PD-L1 expression, post treatment TIL infiltration, change in PD-L1 expression and circulating tumor cell response. Overall assessment of time to progression and survival will also be summarized for each cohort. Assuming no untoward adverse effects from the combination of Vigil with atezolizumab, the treatment of 20-25 patients should be sufficient to assess safety and provide an estimate of the immune response rate and RECIST response rate.

 Part 1

The first part will be a safety run-in where the initial 3 subjects registered will receive the combination of Vigil plus atezolizumab. Part 1 will evaluate the safety of Vigil in combination with atezolizumab.

Vigil immunotherapy will be administered at a concentration of 1x10⁷ cells/dose given via intradermal injection every 3 weeks for a minimum of 4 doses and a maximum of 12 doses. Atezolizumab will be administered at the FDA approved dose and schedule as described in the U.S. Package Insert (USPI). Thus, atezolizumab is to be administered at a dose of 1200 mg as an intravenous infusion every 3 weeks. The initial dose is to be administered over one hour and if well tolerated, subsequent infusions may be administered over 30 minutes. Vigil should be administered first, followed 30 minutes later by atezolizumab.

The first subject to receive the combination of Vigil plus atezolizumab must complete the first 21-day cycle of combination therapy without serious, unexpected toxicity before the enrollment of any patients into Part 2 can occur.

Part 2

Part 2 is a randomized, open label intra-patient crossover study of Vigil, the checkpoint inhibitor atezolizumab and the combination of the two agents. Eligible patients will be randomized to receive two cycles of Vigil alone or two cycles of atezolizumab alone, followed by combination treatment with both agents.

Vigil immunotherapy will be administered at a concentration of 1×10^6 or 1×10^7 cells/dose given via intradermal injection every 3 weeks for a minimum of 4 doses and a maximum of 12 doses.

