6.0 INVESTIGATIONAL PLAN

6.1 Subject Screening and Registration

Written documentation of full, unconditional IRB approval of the protocol and consent document must be on file before a subject can be screened. Study participation begins once written informed consent is obtained.

The Research Nurse or Clinical Research Coordinator will register the subject via email addressed to the Sponsor.

Please allow 48 hours for subject registration as the subject's source documents will be reviewed to ensure they meet the inclusion/exclusion criteria. Once confirmed, the site will be notified of eligibility by the Sponsor.

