- Events suggestive of hypersensitivity, infusion-related reactions, cytokine release syndrome, influenza-like illness, systemic inflammatory response syndrome, and systemic immune activation
- Nephritis
- Ocular toxicities (e.g., uveitis, retinitis)
- Myositis
- Myopathies, including rhabdomyolysis
- Grade \geq 2 cardiac disorders (e.g., atrial fibrillation, myocarditis, pericarditis)

Criteria for Hy's Law (FDA Guidance 2009)

- The drug causes hepatocellular injury, generally shown by a higher incidence of 3-fold or greater elevations above the ULN of ALT or AST than the (non-hepatotoxic) control drug
- Among trial subjects showing such aminotransferase elevations, often with aminotransferases much greater than 3 x ULN, one or more also show elevation of serum total bilirubin to >2 x ULN, without initial findings of cholestasis (elevated serum alkaline phosphatase)
- No other reason can be found to explain the combination of increased aminotransferases and total bilirubin, such as viral hepatitis A, B, or C; pre-existing or acute liver disease; or another drug capable of causing the observed injury.

Unexpected Adverse Event

An unexpected event is any AE that is not identified in nature, severity or frequency in the Clinical Investigator's brochure or the drug package insert.

Grading Adverse Events

Adverse events (AEs) will be recorded throughout the trial. Toxicities and AEs will be graded and reported using the Common Toxicity Criteria for Adverse Events (CTCAE) Version 4.03 as linked in Appendix D.

Adverse events will be summarized using the MedDRA coding system or higher. The NCI-CTCAE will be used for AE grading. All AEs, regardless of severity, will be followed by the Treating Physician until resolution is satisfactory.

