14.2 Atezolizumab Infusion Reactions

Severe infusion reactions have occurred in patients in clinical trials of atezolizumab. Infusion related reactions occurred in 1.3% (25/1978) of patients across clinical trials, 1.7% (9/523) of patients with urothelial carcinoma, and 1.6% (16/1027) of patients with NSCLC. Interrupt or slow the rate of infusion in patients with mild or moderate infusion reactions. Permanently discontinue atezolizumab in patients with Grade 3 or 4 infusion reactions.

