14.3 Risks Associated with Atezolizumab

Refer to the Atezolizumab Investigator's Brochure for a detailed description of anticipated safety risks for atezolizumab.

Systemic immune activation is a rare condition characterized by an excessive immune response. Given the mechanism of action of atezolizumab, systemic immune activation is considered a potential risk when given in combination with other immunomodulating agents. Systemic immune activation should be included in the differential diagnosis for patients who, in the absence of an alternative etiology, develop a sepsis-like syndrome after administration of atezolizumab, and the initial evaluation should include the following:

- CBC with peripheral smear
- PT, PTT, fibrinogen, and D-dimer
- Ferritin
- Triglycerides
- AST, ALT, and total bilirubin
- LDH
- Complete neurologic and abdominal examination (assess for hepatosplenomegaly)

If systemic immune activation is still suspected after the initial evaluation, contact the Medical Monitor for additional recommendations.

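### Part 2 opens on one run-in subject's first cycle and a serious-and-unexpected criterion; no study-level decision on the rest of the run-in is required before Part 2 combination dosing

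*Combined protocol and SAP*

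**What the plan says.** The Synopsis and Section 4.0 describe Part 1 in the same terms: "The first part will be a safety run-in where the initial 3 subjects registered will receive the combination of Vigil plus atezolizumab". The condition for moving on is that "The first subject to receive the combination of Vigil plus atezolizumab must complete the first 21-day cycle of combination therapy without serious, unexpected toxicity", and this must happen "before the enrollment of any patients into Part 2 can occur". Part 2 subjects are randomised to "two cycles of Vigil alone or two cycles of atezolizumab alone, followed by combination treatment with both agents", so their combination dosing starts at cycle 3.

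Section 14.0 defines the key word: "An unexpected event is any AE that is not identified in nature, severity or frequency in the Clinical" Investigator's brochure or the package insert. An event must therefore be both serious and outside those listings to count.

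The other safeguards work at a different level:

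- Sections 5.6 and 6.2.2 hold or stop treatment for the individual patient.
- Section 14.6 sends SAEs and AESIs to the sponsor within 24 hours, and Section 7.2 sends SAE reports to the IRB.
- Section 5.6 names sponsor discontinuation of the protocol as a reason for coming off treatment, without criteria.
- The review at registration in Section 6.1 concerns eligibility: the subject's "source documents will be reviewed to ensure they meet the inclusion/exclusion criteria".

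No section defines a dose-limiting toxicity, a safety committee, a required review of run-in subjects 2 and 3, or a check before Part 2 cycle 3.

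**The concern.** Combination safety is the primary objective, and three subjects are treated first in order to evaluate it. Followed to the letter, the plan lets two of those three inform no decision before Part 2 subjects receive the combination. Section 4.0 also bases the adequacy of 20-25 patients on there being no untoward effects from the combination, but names no point at which anyone must confirm this.

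The expectedness limit matters most for risks the protocol already recognises. Section 14.2 says "Severe infusion reactions have occurred in patients in clinical trials of atezolizumab", and Section 14.3 says "systemic immune activation is considered a potential risk when given in combination with other immunomodulating agents". If the brochure or insert lists such an event at the severity seen, its occurrence in subject 1 would leave Part 2 open. A Grade 3 or 4 event attributed to Vigil would probably count as unexpected, since Section 1.4 reports none to date.

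At stake is whether a safety signal that the sponsor holds must lead to a recorded decision, or only may.

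**Working it through.** The plan gives no toxicity threshold, error rate or combination event rate, so there is no figure of its own to reproduce. The event rates in steps 3 and 4 are assumptions.

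**1. What the opening condition uses**

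| Run-in finding in cycle 1 | Study-level consequence in the plan |
|---|---|
| Subject 1, serious and unexpected | Part 2 cannot enrol |
| Subject 1, serious but listed | None stated |
| Subject 2 or 3, any event | None stated |

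**2. Would the data exist in time?** Inputs: 21-day cycles (Section 6.2.1), two single-agent cycles in Part 2 (Section 4.0), a ±5 day visit window and a screening window of 2 weeks (Appendix B). The first three subjects registered go into Part 1, so no Part 2 subject is registered before subject 3.

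Count days from subject 3's registration, and let d be the day of that subject's first dose. Cycle 1 ends on day d + 21. Allow 7 days for review, which gives day d + 28. In the extreme case a Part 2 subject is registered and dosed on day 0. That subject's cycle 3 falls on day 2 × 21 = 42, or day 37 if the full window is used.

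- Margin between data and Part 2 cycle 3: 42 − (d + 21) = 21 − d days, or 16 − d with the window.
- Hold needed for the review: max(0, d + 28 − 42) = max(0, d − 14) days, or max(0, d − 9) with the window.

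| d (assumed) | Data margin, nominal / window | Hold, nominal / window |
|---|---|---|
| 14 | 7 / 2 days | 0 / 5 days |
| 21 | 0 / −5 days | 7 / 12 days |
| 28 | −7 / −12 days | 14 / 19 days |

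If subject 3 starts within the 2-week screening window, the cycle 1 data precede every Part 2 combination dose. A late start by subject 3 reverses this.

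**3. How much do three subjects say compared with one?** With no events in n subjects, the exact one-sided 95% upper limit is 1 − 0.05^(1/n).

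- n = 1: 1 − 0.05 = 0.95
- n = 3: 1 − 0.05^(1/3) = 0.632

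Both limits are wide.

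**4. How often would a rule based on three subjects act?** The chance of at least one event in three is 1 − (1 − p)³.

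| Assumed rate p of related Grade 3+ or serious events | Chance of a trigger in run-in cycle 1 |
|---|---|
| 2% | 5.9% |
| 5% | 14.3% |
| 10% | 27.1% |
| 20% | 48.8% |
| 30% | 65.7% |

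The present condition closes Part 2 with probability equal to the serious-and-unexpected rate in one subject. That is a narrower set of events, so the two probabilities should not be set against each other at the same p.

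A pass/fail rule on three subjects would not clearly be better. At p = 30% for the same events, the one-subject rule passes with probability 0.70. Allowing at most one event in three passes with probability 0.7³ + 3 × 0.3 × 0.7² = 0.784. Requiring none in three passes with probability 0.7³ = 0.343. This favours a required decision over an automatic stop.

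**The case against.** The strongest reply is that the sponsor will see these events anyway. Section 14.0 lists infusion-related reactions and systemic immune activation by name as AESIs and says an AESI may be serious or non-serious. Section 14.6 requires reporting within 24 hours, and Section 14.3 adds a work-up and contact with the Medical Monitor if systemic immune activation is still suspected. There is no dose escalation: atezolizumab is at its approved dose, and over 160 patients have had Vigil with no attributed Grade 3 or 4 event (upper limit about 1 − 0.05^(1/160) = 1.9%, for Vigil alone). Patient-level stopping rules are strict. All of this stands, and it lowers the practical risk. It does not supply a decision: no report leads by rule to a pause, a review or a recorded conclusion.

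It is also fair that the reach of the expectedness limit is unknown. The brochure and insert are not among the documents, and the definition covers severity and frequency as well as nature, so an unusually severe form of a listed event could still count.

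A reader might infer that the planned Part 2 subjects (20 − 3 = 17 to 25 − 3 = 22, before any re-enrolment) will receive the combination before subjects 2 and 3 have been observed. The documents do not support that. Registration order and the two single-agent cycles normally put the run-in data first. Nor do the assumed rates above demonstrate an excess of harm.

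**Conclusion.** The point holds as a weakness in the stated rule. One subject, one cycle and a serious-and-unexpected criterion are the only study-level check before the combination is given more widely, and no required decision uses the rest of the run-in. It is neither a lack of data nor a demonstrated exposure of Part 2 subjects.

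The size is modest. Three subjects remain a weak screen, with an upper limit of 63% after no events against 95% for one. The gain lies mainly in widening the criterion and obliging someone to decide. The conclusion that data arrive in time assumes that subject 3 is dosed within about two weeks of registration. How much the expectedness limit excludes depends on listings that the documents do not show. This is a cheap improvement worth making.

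**What to change.** Keep the first-subject rule for opening Part 2 enrolment, and add to the Synopsis and Section 4.0:

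> No Part 2 subject receives the cycle 3 combination dose until all three Part 1 subjects have completed cycle 1 (or stopped for toxicity) and the Medical Monitor has documented a review of all Part 1 safety data available at that time. Any treatment-related Grade 3 or higher or serious event, whether or not expected, requires a documented decision to proceed, amend or stop within 7 days of its report, before further Part 2 combination dosing. A cycle held for this review is delayed, not skipped, and is exempt from the three-day limit in Section 6.2.2.

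Add a cross-reference in Section 6.2.2. No new data are needed. Compliance can be checked where Section 10.2 already has sponsor quality staff confirm Medical Monitor approval before Vigil is shipped.

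Costs:

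- A hold of about 0 to 5 days if subject 3 is dosed within 14 days of registration and the review takes 7 days. It is longer, and off study treatment, if subject 3 starts later.
- Some pauses for a regimen that proves acceptable: 27% in run-in cycle 1 at an assumed 10% related-event rate. There will be more over time, because the trigger is not limited to that cycle.
- No added independence, since the reviewer is the sponsor's own Medical Monitor.

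If Part 1 is already complete, a dated review of its three subjects serves the first sentence.

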5.0 STUDY POPULATION

5.1 Sample Size

Approximately 20-25 subjects will be enrolled.

5.2 Tissue Procurement Inclusion Criteria:

Subjects will be eligible for tissue procurement for the Vigil manufacturing process, if they meet all of the following criteria:

- 1. Histologically confirmed Stage IIIb, IIIc or IV high-grade papillary serous, clear cell, or endometrioid ovarian, fallopian tube or primary peritoneal carcinoma
- 2. Age \geq 18 years.
- 3. Estimated survival \geq 6 months.
- 4. ECOG Performance Status ≤ 1
- 5. Metastatic disease
- Planned standard of care surgical procedure (e.g., tumor biopsy or palliative resection or thoracentesis) and expected availability of a cumulative soft-tissue mass of ~10-30 grams tissue ("grape" to "golf-ball" size) or ascites fluid estimated volume ≥ 500mL (from a primary or secondary paracentesis, yielding in a high volume of tumor cells) for immunotherapy manufacture.
- 7. Tumor intended for immunotherapy manufacture is not embedded in bone and does not contain luminal tissue (e.g. bowel, ureter, bile duct).
- 8. Ability to understand and the willingness to sign a written informed protocol specific consent for tissue harvest or a parental/guardian informed consent and pediatric assent when appropriate.

5.3 Tissue Procurement Exclusion Criteria:

Subjects meeting any of the following criteria are not eligible for tissue procurement for the Vigil manufacturing:

- Medical condition requiring any form of chronic systemic immunosuppressive therapy (steroid or other) except physiologic replacement doses of hydrocortisone or equivalent (no more than 30 mg hydrocortisone or 10 mg prednisone equivalent daily) for < 30 days duration.
- Known history of other malignancy unless having undergone curative intent therapy without evidence of that disease for ≥ 3 years except cutaneous squamous cell and basal cell skin cancer, superficial bladder cancer, in situ cervical cancer or other in situ cancers are allowed if definitively resected.

- 3. Brain metastases unless treated with curative intent (gamma knife or surgical resection) and without evidence of progression for ≥ 2 months.
- 4. Any documented history of autoimmune disease with exception of Type 1 diabetes on stable insulin regimen, hypothyroidism on stable dose of replacement thyroid medication, vitiligo, or asthma not requiring systemic steroids.
- 5. Known HIV or chronic Hepatitis B or C infection.
- 6. Known history of allergies or sensitivities to gentamicin.

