- Treatment delay not related to toxic events (including subjects unable to adhere to dose schedule) may not extend for more than three days unless due to symptoms related to disease or infection in which case up to a 4-week delay is allowed.
- If ≥ one 2-week delay due to disease or infection occurs, subject status must be reviewed by sponsor.

Atezolizumab should be permanently discontinued for any of the following AEs:

- Any life-threatening or Grade 4 AE
- Grade 3 or 4 pneumonitis
- Aspartate aminotransferase (AST) or alanine aminotransferase (ALT) >5 times upper limit of normal or total bilirubin >3 times upper limit of normal
- Diarrhea with abdominal pain, fever, ileus, or peritoneal signs; increase in stool frequency (Grade 4) stool incontinence, need for intravenous hydration for more than 24 hours, gastrointestinal hemorrhage, and gastrointestinal perforation
- Grade 4 hypophysitis
- Myasthenic syndrome/myasthenia gravis, Guillain-Barré or meningoencephalitis (all grades)
- Grade 3 or 4 ocular inflammatory toxicity
- Grade 4 or any grade of recurrent pancreatitis
- Grade 3 or 4 infusion-related reactions
- Grade 4 rash
- Grade 3 or 4 nephritis
- Myocarditis (all grades)

For combination treatment, the occurrence of a Grade 3 or 4 toxicity attributed to Vigil will result in the cessation of Vigil dosing and continuation of single agent atezolizumab only.

Please reference https://www.gene.com/download/pdf/tecentrig_prescribing.pdf for full prescribing information regarding atezolizumab.

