14.6 Serious Adverse Event Reporting

All SAEs and AESIs will be reported within 24 hours of notification by the site via email or fax to Gradalis, Inc. This includes any death from any cause while a subject is receiving the study agent on this protocol, or \leq 30 days following the last dose of the protocol study agent.

The site will supply as much information as is available at the time of the initial SAE or AESI reporting (study number, subject study number, onset date, relationship, subject demographics, event, dosing regimen of study agent). All SAEs or AESIs must be followed until resolution.

Gradalis, Inc.				
[name] [contact]				
Direct: [contact]	[contact]			

Gradalis, Inc. and Genentech, Inc. will report adverse events to the FDA in compliance with 21 CFR 312.32.

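### No prespecified study-level toxicity criterion applies once Part 2 opens, so a too-toxic combination could run to full enrolment unless the sponsor chooses to halt

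*Combined protocol and SAP*

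**What the plan says.** Section 5.1 states: "Approximately 20-25 subjects will be enrolled". Section 4.0 describes Part 1 as a "safety run-in where the initial 3 subjects registered will receive the combination of Vigil plus atezolizumab". One study-level condition follows: the first of these subjects must finish one 21-day cycle free of toxicity that is both serious and unexpected before Part 2 may enrol. It applies once and does not wait for run-in subjects 2 and 3. Section 14.0 counts an event as unexpected only if the brochure or package insert does not already describe it.

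In Part 2 subjects are "randomized to receive two cycles of Vigil alone or two cycles of atezolizumab alone, followed by combination treatment with both agents", so the combination begins at Cycle 3. Section 4.0 adds: "Assuming no untoward adverse effects from the combination of Vigil with atezolizumab, the treatment of 20-25 patients should be sufficient to assess safety". Section 14.3 says that "systemic immune activation is considered a potential risk when given in combination with other immunomodulating agents".

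The remaining toxicity rules are the withdrawal list in 5.6, the hold and permanent-discontinuation lists in 6.2.2, and the rule that a "Grade 3 or 4 toxicity attributed to Vigil will result in the cessation of Vigil dosing and continuation of single agent atezolizumab only". Item 12 of 5.6 lists the sponsor ending the protocol as a reason for coming off treatment, with no criterion attached. Section 14.6 provides that "All SAEs and AESIs will be reported within 24 hours of notification by the site". Section 16.1 plans descriptive adverse event summaries, and 16.3 says the sample size has no statistical basis.

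**The concern.** The primary objective is the safety of the combination, and most subjects who receive it will do so in Part 2. There the second agent is added after two doses of the first, in either order. Part 1 observes neither situation.

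The claim that 20-25 patients suffice is conditional on there being no untoward effects from the combination. After Part 2 opens, nothing in the plan tests that condition against accumulating data. Withdrawal, holding and cessation rules protect the subject who has the event; they do not protect the next one to be randomised. If severe related toxicity were frequent, the documents do not say at what count anyone must stop and look, who looks, or whether the two sequences are looked at separately.

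**Working it through.** **Inputs from the documents.** Total enrolment 20-25 (5.1); run-in 3 (4.0); cycle length 21 days (6.2.1); combination from Cycle 3 in Part 2 (4.0, Appendix B). The plan states no toxicity limit, boundary, error rate, allocation ratio or accrual rate, and 16.3 gives no formula for N, so there is no planned operating characteristic to reproduce.

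**Part 2 size.** 20 − 3 = 17 and 25 − 3 = 22, if the total includes the run-in and re-enrolled subjects are not counted twice.

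**What Part 1 can exclude.** The one-sided 95% upper bound on the event rate after 0 of n is 1 − 0.05^(1/n). That is 95% for n = 1 (the opening condition) and 63% for n = 3.

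**Time to an outcome.** Two lead-in cycles take 2 × 3 = 6 weeks and one combination cycle takes 3 weeks, so each Part 2 outcome is known 9 weeks after entry.

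**As written.** The prespecified chance of a pause is 0 at any toxicity rate. Expected subjects with an event, N × p, if enrolment completes and all reach the combination:
- at 40%: 17 × 0.4 = 6.8; 22 × 0.4 = 8.8
- at 50%: 17 × 0.5 = 8.5; 22 × 0.5 = 11.0

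**Illustrative boundary (all rates assumed).** Tolerated rate 20%. After each subject, pause if the cumulative count is so high that its binomial tail at 20% is at most 0.038. This value keeps the overall false-pause chance below 10%. The boundary is 3 events in the first 3-4 subjects, 4 in 5-7, 5 in 8-10, 6 in 11-13, 7 in 14-17, 8 in 18-20 and 9 in 21-22. Exact recursion, with each outcome known before the next entry:

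| True rate | P(pause), N=22 | Mean treated | Mean events | P(pause), N=17 |
|---|---|---|---|---|
| 20% | 0.09 | 20.9 | 4.2 | 0.08 |
| 30% | 0.35 | 18.0 | 5.4 | 0.31 |
| 40% | 0.69 | 13.6 | 5.4 | 0.63 |
| 50% | 0.92 | 9.5 | 4.8 | 0.87 |

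Tuned the same way for N=22, a tolerated rate of 10% gives 0.84 at 30% and 0.97 at 40%. A tolerated rate of 30% gives 0.63 at 50% and 0.89 at 60%.

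**With the 9-week lag.** Same boundary, N=22, pausing randomisation only, 20,000 simulated trials per setting, evenly spaced entries (spacing assumed). Mean number randomised, with the chance that the pause comes before the last entry in brackets:

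| True rate | One entry per week | Every 2 weeks | Every 4 weeks |
|---|---|---|---|
| 40% | 18.5 (0.51) | 16.3 (0.62) | 15.0 (0.65) |
| 50% | 16.3 (0.77) | 13.2 (0.87) | 11.3 (0.88) |

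For N=17 and weekly entry the means are 15.7 at 40% and 14.8 at 50%.

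**Pooling.** Suppose simple 1:1 allocation (assumed), 50% toxicity in one sequence and 20% in the other. The pooled rate is (50 + 20)/2 = 35%, so the pooled chance of a pause for N=22 lies between 0.35 and 0.69, not at 0.92. A pooled count alone can miss a problem confined to one sequence.

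**The case against.** A reader might infer that the plan would carry a too-toxic combination to full enrolment whatever happened. The documents do not support that. The sponsor may end the protocol (5.6 item 12), receives serious and special-interest events within 24 hours (14.6), confirms each registration (6.1), and ships Vigil only once the Medical Monitor has approved eligibility (10.2). Systemic immune activation is itself a special-interest event (14.0) with a work-up and Medical Monitor contact (14.3), and the IRB receives serious event reports and re-approves at least yearly (7.2). A halt is therefore available. What stands is that none of these provisions carries a threshold, so whether and when a halt occurs is discretionary.

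Nor does every Part 2 subject first meet the combination there. Section 4.0 lets subjects previously given Vigil on this study re-enrol into Part 2, and some may already have had both agents. Others may leave before Cycle 3, so the expected event counts above are upper-end figures.

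The 40-50% rates should not be read as a forecast. Section 1.4 reports no Grade 3 or 4 event attributed to Vigil in over 160 treated patients, and atezolizumab is given at its labelled dose. These are reasons to expect lower rates, but they come from single-agent experience and do not settle the safety of the combination, which is what the trial exists to measure.

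Three practical objections also stand and shape the remedy. A pooled boundary dilutes a sequence-specific signal. The 24-hour reports omit severe events that are neither serious nor of special interest. Pausing doses in subjects already randomised would conflict with 6.2.2, which limits most non-toxicity delays to three days.

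**Conclusion.** The gap is real and worth correcting. After a one-time condition resting on one subject, no prespecified study-level toxicity criterion governs the roughly 17-22 Part 2 subjects, most of whom first receive the combination in sequences that Part 1 does not run. Full enrolment of a too-toxic combination is possible, not certain.

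Under the no-lag assumptions, a simple boundary raises the prespecified chance of a pause at N=22 from 0 to 0.69 at 40% and 0.92 at 50%, and cuts expected events from 8.8 to 5.4 and from 11.0 to 4.8. These are best-case figures: with weekly entry and the 9-week lag, 18.5 or 16.3 of 22 subjects would still be randomised on average. The conclusion that a criterion is missing depends on none of the assumed rates; the size of the benefit depends on all of them and on accrual.

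**What to change.** Add to Section 4.0 (Part 2) and Section 16.1 a sequential monitoring boundary on the cumulative number of subjects with treatment-related severe toxicity through the first combination cycle.

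- **Review:** the existing Medical Monitor reviews the count overall and by sequence, from the serious and special-interest event reports plus the adverse event data in the eCRF.
- **Consequence:** crossing the boundary pauses further randomisation until the sponsor has reviewed the data.
- **Inputs:** the sponsor's clinical team sets the event definition and the tolerated rate. The 20% used above is an illustration, not a proposal.
- **Operating characteristics:** the statistician tabulates them for N=17 and N=22, overall and by sequence, at the expected accrual rate and allowing for the 6-week lead-in plus one combination cycle.
- **Subjects already randomised:** what happens to their dosing is left to the clinical team, who must reconcile any pause with the delay limits in 6.2.2.

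The cost is an amendment with a boundary table, and timely entry and review of eCRF adverse events, which the 24-hour reports do not replace. No new committee or visit is needed. The downside is up to about a 10% chance of an unnecessary temporary pause when toxicity is at the tolerated rate; separate by-sequence boundaries would add to that and should be included in the table.
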